6.3. Secondary Efficacy Endpoints

6.3.1. Definition of the Secondary Efficacy Endpoints

The secondary efficacy endpoints are:

- Change from baseline in terminal ileum segmental MaRIA score at Week 24
- Change from baseline in distal ileum segmental MaRIA score at Week 24

- Change from baseline in jejunum segmental MaRIA score at Week 24
- Proportion of subjects achieving MaRIA remission in terminal ileum segment at Week 24
- Proportion of subjects achieving MaRIA remission in distal ileum segment at Week 24
- Proportion of subjects achieving MaRIA remission in jejunum segment at Week 24
- Proportion of subjects achieving MaRIA response in terminal ileum segment at Week 24
- Proportion of subjects achieving MaRIA response in distal ileum segment at Week 24
- Proportion of subjects achieving MaRIA response in jejunum segment at Week 24
- Proportion of subjects achieving subject level small bowel MaRIA remission at Week 24
- Proportion of subjects achieving subject level small bowel MaRIA response at Week 24
- Proportion of subjects achieving early clinical remission by CDAI at Week 10
- Change from baseline in CDAI scores at Week 10
- Change from baseline in CDAI scores at Week 24

Refer to [Table 6-1](#) for dichotomous secondary endpoints definitions.

6.3.2. Analysis of the Secondary Efficacy Endpoints

For binary endpoints, the same statistical analysis methods described in Section [6.2.2](#) for analyzing the primary efficacy endpoint will be utilized.

Continuous endpoints will be summarized using descriptive statistics (n, mean, SD, median, Q1, Q3, minimum, maximum) by treatment group and analysis visit.

An analysis of covariance (ANCOVA) model that includes treatment (filgotinib 200 mg, filgotinib 100 mg, or placebo), stratification factors as fixed-effect factors, and baseline value as covariates will also be implemented. The estimated means of treatment effects and estimated differences in treatment effects between each filgotinib dose group and placebo will be presented with 90% CIs. Before the ANCOVA model is conducted, the following imputation will be performed:

- For change from baseline in segmental MaRIA score, if segmental MaRIA score is missing at Week 24, then corresponding segmental MaRIA score at baseline will be used to impute the missing value.
- For change from baseline in CDAI score, any missing CDAI component score will be imputed by LOCF method using the previous valid component score calculated at most recent analysis visit (eg, use the component score from Week 6 to impute missing component at Week 10, or use the component score from Week 18 to impute missing component at Week 24). If the component score from the most recent analysis visit is also missing, the missing value will be imputed with corresponding component score at baseline.

The observed mean change from baseline values for CDAI scores will be summarized and plotted over all analysis visits by treatment group.

In addition, subjects' small bowel disease status (remission, response, stable, and progression) based on MaRIA score will be summarized by treatment group for Week 24. A detailed definition of disease status in MaRIA score is provided in definition of terms.

CCI

CCI

A series of 12 horizontal black bars of varying lengths, decreasing from left to right. Each bar is preceded by a small black vertical tick mark.

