3.5. Missing Data and Outliers

3.5.1. Missing Data

In general, missing data will not be imputed unless methods for handling missing data are specified. Exceptions are presented in this document.

For missing last dosing date of study drug, imputation rules are described in Section 4.2.1. Imputation and calculation rules for missing patient diary data and other CDAI components are described in [Appendix 3](#). Imputation and calculation rules for missing MaRIA data are described in Section 6.3. The handling of missing or incomplete dates for AE onset is described in Section 7.1.5.2, and for prior and concomitant medications in Section 7.4.

Values for missing safety laboratory data will not be imputed. However, a missing baseline result will be replaced with a screening result, if available. If no pre-treatment laboratory value is available, the baseline value will be assumed to be normal (ie, no grade) for the summary of graded laboratory abnormalities. If safety laboratory results for a subject are missing for any reason at a time point, the subject will be excluded from the calculation of summary statistics for that time point.

Values for missing vital signs data will not be imputed. However, a missing baseline result will be replaced with a screening result, if available.

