3.7.2. Analysis Visit Windows

Subject visits may not occur on protocol-specified days. Therefore, for the purpose of analysis, observations will be assigned to analysis windows.

The analysis windows for efficacy endpoints including CDAI, PRO2, **CCI** endpoints are based on study day and are provided in [Table 3-1](#).

The analysis windows for MaRIA score-related efficacy endpoints are based on study day and provided in [Table 3-2](#).

The analysis windows for body weight, vital signs, ECG, safety laboratory parameters (hematology, chemistry, fasting lipid profile, and serum immunoglobulin), **CCI** are provided in

[Table 3-3](#).

Table 3-1 Analysis Visit Windows for CDAI, PRO2 CCI -related Endpoints

Nominal Visit	Analysis Visit	Nominal Day (Study Day)	Lower Limit (Study Day)	Upper Limit (Study Day)
Screening/Day 1	Baseline	1	(none)	1
Week 2	Week 2	15	2	22
Week 4	Week 4	29	23	36
Week 6	Week 6	43	37	57
Week 10	Week 10	71	58	85
Week 14	Week 14	99	86	113
Week 18	Week 18	127	114	141
Week 24	Week 24	169	142	197

Note: For analysis purpose, PRO2 from Screening and Visit Day 1 will be calculated and both visits will be considered for the derivation of baseline, which is defined as the last available observation on or prior to the first dosing date of the study drug.

CCI

Table 3-2 Analysis Visit Windows for MaRIA Score-related Efficacy Endpoints

Nominal Visit	Analysis Visit	Nominal Day (Study Day)	Lower Limit (Study Day)	Upper Limit (Study Day)
Screening	Baseline	1	(none)	1
Week 24	Week 24	169	142	197

Table 3-3 Analysis Visit Windows for Body Weight, Vital Signs, ECG, Hematology, Chemistry, Fasting Lipid Profile, Serum Immunoglobulin, CCI CCI

Nominal Visit	Analysis Visit	Nominal Day (Study Day)	Lower Limit (Study Day)	Upper Limit (Study Day)
Screening/Day 1	Baseline	1	(none)	1
Week 2	Week 2	15	2	22
Week 4	Week 4	29	23	36
Week 6	Week 6	43	37	57
Week 10	Week 10	71	58	85
Week 14	Week 14	99	86	113
Week 18	Week 18	127	114	141
Week 24	Week 24	169	142	≥ 169

Note: ECG is collected postbaseline at Week 10 and the corresponding analysis windows will be applied; fasting lipid profile, CCI are collected postbaseline at Weeks 10 and 24 and the corresponding analysis windows will be applied; serum immunoglobulin is collected postbaseline at Weeks 4, 10, and 24 and the corresponding analysis windows will be applied.

An unscheduled visit prior to the first dosing of study drug may be included in the calculation of the baseline value, if applicable.

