Secondary	Subject level small bowel MaRIA remission at Week 24	MaRIA score < 7 at Week 24 in each of the 3 small bowel segments: terminal ileum, distal ileum, and jejunum, among subjects with MaRIA score ≥ 7 in at least 1 small bowel segment at Baseline
Secondary	Subject level small bowel MaRIA response at Week 24	All small bowel segments with Baseline MaRIA score ≥ 7 achieve segment level MaRIA response, with no segment level disease worsening in any other segment(s) at Week 24, among subjects with MaRIA score ≥ 7 in at least 1 small bowel segment at Baseline
Secondary	Early Clinical remission by CDAI at Week 10	CDAI score < 150 points at Week 10

Summary of Dichotomous Efficacy Endpoints

Numbers and percentages of subjects achieving each of the dichotomous efficacy endpoints defined above, and numbers and percentages of subjects not achieving those endpoints for the following reasons will be summarized by treatment, in a hierarchy order with the first reason being the highest.

- 1) Subjects who do not meet the endpoint based on observed data
- 2) Subjects who do not meet the endpoint due to study treatment failure
- 3) Subjects who are protocol-specified CDAI non-responders at Week 10 and discontinued study drug

- 4) Subjects who do not meet the endpoint due to study drug discontinuation led by protocol-specified disease worsening
- 5) Subjects who do not have sufficient measurements to determine the endpoint due to study drug discontinuation for other reasons
- 6) Subjects who do not have sufficient measurements to determine the endpoint while on study drug

Non-Responder Imputation

For analysis of binary efficacy endpoints defined in [Table 6-1](#), subjects who do not have sufficient measurements due to any reason (including treatment failures and CDAI non-responders at Week 10) to determine the endpoint will be considered non-responders (ie, non-responder imputation [NRI]).

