6.1.1. Calculation of CDAI and PRO2 Scores

The CDAI system is a composite index of 8 disease activity variables (components) with scores ranging from 0 to over 600 based upon a composite of symptoms (eg, abdominal pain), signs (the presence of abdominal mass and body weight), laboratory values (eg, hematocrit), and physician assessment amongst others. The CDAI has 3 patient reported outcome components: liquid or very soft stool frequency, abdominal pain, and general wellbeing. The clinical remission by CDAI endpoint is defined by the CDAI score, calculated as a weighted sum of all 8 component subscores.

If subjects have 3 or more of the 8 component subscores missing, then the subjects will be considered as having insufficient data to determine response status and their CDAI score will be considered missing. If subjects have 1 or 2 CDAI components missing, then the missing component will be imputed by the Last Observation Carrying Forward (LOCF) method using the previous valid component score calculated at the most recent analysis visit (eg, use the component score from Week 6 to impute missing component at Week 10, or use the component score from Week 18 to impute missing component at Week 24). If the component score from the most recent analysis visit is also missing, the missing value will be imputed with corresponding component score at baseline.

The PRO2 has 2 patient reported outcome components: liquid or very soft stool frequency subscore and abdominal pain subscore. If either subscore is missing, no imputation will be done.

For further information on CDAI, PRO2, and calculation rules at screening and post-screening, refer to [Appendix 3](#).

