Rounding of subscores into one decimal place is for displaying purpose only. When calculating the CDAI scores, the subscores will not be rounded.

- 4) The CDAI score for a specific visit is based on a weighted sum (rounded to the nearest integer) of all 8 components. The CDAI score will be set to 0 in the case the calculation leads to a CDAI score of < 0. Each component will be selected within the analysis window as defined in Section [3.7.2](#).
 - a) If subjects have 3 or more of the 8 CDAI components missing, then the subjects will be considered as having insufficient data to determine response status and their CDAI score will be considered missing. If at least 1 out of the 6 complications under the complication component is missing, then the complication component will be considered missing.
 - b) If subjects have 1 or 2 components missing, then the missing component will be imputed by the LOCF method using the previous valid component score calculated at most recent analysis visit (eg, use the component score from Week 6 to impute missing component at Week 10, or use the component score from Week 18 to impute missing component at Week 24). If the component score from the most recent analysis visit is also missing, the missing value will be imputed with corresponding component score at baseline.
- 5) The PRO2 subscores for a specific visit are based on the evaluation of liquid or very soft stool frequency and abdominal pain subscores individually (rounded to the nearest integer) within the analysis window as defined in Section [3.7.2](#). If either subscore is missing, no imputation will be done.

Source of Information Used for Calculation

The sources of information used for the calculations of CDAI and PRO2 scores as described above are given in [Table 13-5](#) (the calculated scores from ERT data will not be used for data analysis). Hematocrit collected from local laboratory and weight measured at home due to COVID-19 impact will be used in CDAI calculation.

Table 13-5. Sources of Information for Calculating CDAI and PRO2 Scores

Variable in Calculation	Data Source
MRE Procedure Date	MREDAT in MRE dataset from eCRF data for Screening and Week 24
Lower Endoscopy Procedure Date	QSORRES in CDAI dataset with QSTEST “Date of Procedure” from vendor ERT data
Visit Date	VISITDAT in VISDT dataset from eCRF data
Subject Activation Date on Electronic Device	QSORRES in CDAI dataset with QSTEST “Date of Visit” and Visit “Screening” from vendor ERT data

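### The only visible treatment difference for MaRIA change scores every missing Week 24 scan as no change; unfilled estimates should stand beside it

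*SAP*

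**What the plan says.** - **The fill.** SAP 6.3.2 fits an ANCOVA (treatment, stratification factors, baseline) and reports each filgotinib-versus-placebo difference with a 90% CI. For MaRIA change, before the model is fitted, "if segmental MaRIA score is missing at Week 24, then corresponding segmental MaRIA score at baseline will be used to impute the missing value".
- **Censoring feeds the fill.** SAP Appendix 6 sets efficacy data after treatment failure to missing and overrides other handling rules. A scan taken after failure is therefore also replaced by baseline.
- **When scans exist.** Protocol 6.5 schedules MRE at screening and Week 24 only. The readable early-termination list in Protocol 6.10 has none.
- **Who leaves.** Protocol 3.4, 3.6 and 3.7 require Week 10 non-responders and later worseners to leave blinded treatment.
- **What the protocol foresaw.** Protocol 8.5.2 says last observation carried forward would be considered for missing continuous data.
- **Unfilled output.** SAP 6.3.2 also plans that "Continuous endpoints will be summarized using descriptive statistics (n, mean, SD, median, Q1, Q3, minimum, maximum) by treatment group and analysis visit". SAP 3.5.1 adds that "In general, missing data will not be imputed unless methods for handling missing data are specified", so these summaries read as unfilled. They are per arm; no difference or CI is specified. For the binary endpoints, SAP 6.1 tabulates reasons for not meeting them, including "Subjects who do not have sufficient measurements to determine the endpoint due to study drug discontinuation for other reasons".
- **CDAI change.** SAP 6.3.2 fills any missing component from the preceding analysis visit, and "If the component score from the most recent analysis visit is also missing, the missing value will be imputed with corresponding component score at baseline". SAP 6.1.1 says "If subjects have 3 or more of the 8 component subscores missing, then the subjects will be considered as having insufficient data" and then treats the score as missing; Appendix 3 repeats this.

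**The concern.** The MaRIA difference mixes measured changes with assigned zeros, and the share of zeros can differ by arm. If filgotinib improves CDAI, more placebo subjects will be non-responders, and placebo will probably carry more zeros. A zero is not reliably conservative: a subject whose bowel worsened is also scored zero, and zeros in placebo subjects who would have improved favour the drug. Assigned zeros also add no measurement spread, so the interval is narrower than the scans support.

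There is no hypothesis testing, so estimates and intervals are the whole result. A reader of the one difference with a CI cannot see how much of it was measured.

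For CDAI, a subject with no Week 24 visit gets a score under SAP 6.3.2 but none under 6.1.1, and the SAP does not say outright which applies to the ANCOVA.

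**Working it through.** 1. **The plan's own precision figure.** SAP 1.3 gives a 90% exact CI for 40% remission in 40 subjects. Clopper-Pearson for 16/40 gives 26.94% to 54.22%, matching 26.9% to 54.2%. There is no such figure for MaRIA change, and the documents give no MaRIA SD, expected change or missing rate. Everything below rests on assumed values.

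2. **Formulas.** With share missing m, mean change μ and SD s in those scanned:
   - filled mean = (1 − m)μ
   - filled variance = (1 − m)(s² + mμ²)

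3. **Equal and unequal missingness.**
   - Changes −6.5 and −2.0, 20% missing in both arms: 0.8 × (−4.5) = −3.6 instead of −4.5.
   - Change −6.5 in both arms, 20% drug / 40% placebo missing: −5.2 − (−3.9) = −1.3 instead of 0. Reversing the shares gives +1.3. In simulation (SD 6, 40 vs 20), the filled 90% CI excluded zero in about 20% of runs, against 10% unfilled.

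4. **A plausible missing share.** Protocol 1.4 reports 59% response on 200 mg and 41% on placebo in the earlier study; response meant a CDAI drop of at least 100 points (Protocol 1.2.3.1). With an assumed SD of 90, the mean Week 10 changes are −100 ∓ 0.2275 × 90 = −120.5 and −79.5. Applying this trial's Week 10 rule to simulated CDAI courses gives about 22% non-responders on drug and 36% on placebo (19–25% / 32–39% over SD 70–110 and visit correlation 0.3–0.7). Adding worsening and 5% other exits (0–10%), and assuming leavers have no Week 24 scan, gives about 27% / 40% missing (23–31% / 36–42%). That leaves about 29 of 40 and 12 of 20 scans.

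5. **Effect at 27% / 40%, SD 6.**

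| Mean change, drug / placebo | True difference | Filled, by formula | Filled, simulated | Half-width, filled / observed | Coverage, filled |
|---|---|---|---|---|---|
| −5 / −1 | −4 | −3.65 + 0.60 = −3.05 | −3.07 | 2.51 / 3.57 | 86% |
| −3 / −1 | −2 | −2.19 + 0.60 = −1.59 | −1.60 | 2.41 / 3.57 | 92% |
| −3 / −3 | 0 | −2.19 + 1.80 = −0.39 | −0.39 | 2.41 / 3.56 | 90% |

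   The half-width ratio is 0.68 to 0.70. If MaRIA change correlates 0.5 with CDAI change, the results for true −4, −2 and 0 are:
   - filled: −2.95, −1.48, −0.28 (coverage 84%, 90%, 91%)
   - observed scans: −3.68, −1.70, +0.34
   - multiple imputation using last CDAI: −4.13, −2.14, −0.13

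   Multiple-imputation coverage is 91–92%, with half-widths of 3.6–3.8.

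6. **Where coverage fails.** At 10%/10% and 20%/35% missing (SD 6; the three pairs of mean changes in step 5), filled coverage is 89–92%. At 30%/50% and true −4 it is 85% (SD 8: 88%; SD 4: 78%). At SD 4 and true 0 it is 86%. Step 3's large common change with unequal loss is another exception, at about 80%.

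7. **Uninvolved segments.** Eligibility needs MaRIA ≥ 7 in only one of three segments, and the change endpoints are not restricted to diseased segments. If 40% of subjects (assumed) had disease in a segment and the rest did not change, −5 / −1 becomes −2.0 / −0.4, a difference of −1.6. The filled value is −1.46 + 0.24 = −1.22. Bias falls from 0.95 to 0.38.

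8. **The opposite case.** If unscanned subjects truly do not change, the fill is right. With −3 / −1 among the scanned and 20%/35% missing, the truth is −2.40 + 0.65 = −1.75. Simulated fill gives −1.8 and observed scans −2.05.

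9. **CDAI change.** In the same simulation the full-follow-up difference is −40.3. Filling any missing component gives −36.3; treating scores with 3 or more missing components as missing gives −29.5. The gap is 6.8 points against half-widths of 42 to 47. Carrying the last post-baseline value gives −42.0, and a mixed model −39.6.

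**The case against.** The case for leaving the plan alone is substantial.

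- **It is ordinary LOCF.** With two scheduled scans, baseline is the only value to carry. This stands, and the planned analysis should stay.
- **Zero change is coherent.** The SAP counts missing outcomes as non-response for segment-level binary endpoints, and zero change is a natural continuous counterpart. This stands as a reason for side-by-side reporting rather than replacement.
- **The harm is limited.** Coverage is near nominal in most scenarios, and the bias shrinks where few subjects have disease in a segment. This stands.
- **The simulation favours imputation.** Simulated exit depends mainly on CDAI, so an imputation model containing CDAI does well by construction. This stands; the figures do not show imputation to be best in this trial.
- **Unfilled n, mean and SD are planned.** A reader could build a crude difference, but without baseline or strata adjustment. The plan specifies no such estimate.
- **Redaction.** Text between SAP 6.3.2 and 6.5, and beside Protocol 3.6 and 3.7, is blacked out. The protocol glossary lists MMRM, though no readable protocol text uses it. Further analyses, or scan rules for leavers, may exist.

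A reader might infer that SAP 6.3.2 and 6.1.1 flatly contradict each other on CDAI. The documents do not support that. Section 6.1.1 concerns insufficient data to determine response status; 6.3.2 is written for the change endpoint, and the specific rule most naturally governs. Because 6.1.1 also calls the score itself missing, a confirming sentence is still worth having.

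**Conclusion.** The point holds as a cheap improvement to secondary, descriptive endpoints. The fill can move the MaRIA difference in either direction and narrows its interval. At SD 6 and 27%/40% missing, a true −4 is reported as about −3.1 and a true 0 as about −0.4, with half-widths about 0.7 of those from observed scans. Coverage of the 90% CI departs clearly from nominal only with large effects or within-arm changes, heavy or unequal missingness, or small SD. All sizes depend on the assumed SD, effects and missing shares, and on leavers having no Week 24 scan, which is likely but not stated in the readable text.

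Three stronger readings might be inferred and are not supported:
- **That the fill is an error or a protocol departure.** Protocol 8.5.2 foresaw it.
- **That it threatens the main result.** The primary endpoint is binary and uses non-responder imputation.
- **That the CDAI reset to baseline in SAP 6.3.2 should be replaced.** The same reset stands in SAP 6.1.1 and Appendix 3 for the primary CDAI endpoint. Changing one place would give some subjects two different Week 24 scores, for little simulated gain (−42.0 against −36.3, truth −40.3).

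**What to change.** In SAP 6.3.2:

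1. **MaRIA change.** Keep the baseline-fill ANCOVA. Report beside it, each with 90% CIs, the same ANCOVA on observed scans and a multiple-imputation ANCOVA whose imputation model includes baseline MaRIA, baseline and last CDAI, treatment and the stratification factors. Show the number of Week 24 scans used, by arm and segment, with each estimate. Apply the Appendix 6 censoring to all three as already written.
2. **CDAI change.** Add one sentence confirming that the 6.3.2 rule filling any missing component, and not the 3-or-more rule of 6.1.1 and Appendix 3, governs the ANCOVA. Leave the carry-forward rule unchanged. A mixed model for repeated measures on collected visits is an optional sensitivity analysis.

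The cost is SAP wording and modest programming on data already collected. The downsides are wider supportive intervals, three MaRIA estimates to read together, and a missing-at-random assumption for the imputation and the mixed model. The observed-scan estimate can itself be biased, which is why the three belong side by side.

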6.5. Change from Protocol-Specified Efficacy Analyses

The definitions of the following terms are modified in this SAP:

- In the protocol, the definition of segment level MaRIA response states “For segments with baseline MaRIA score ≥ 15 , a segmental MaRIA score < 11 , or a decrease from baseline in a segmental MaRIA score \geq MDD. For segments with baseline MaRIA score < 15 (but ≥ 7), a segmental MaRIA score < 11 ”.
In the SAP, the definition is modified to “For segments with baseline MaRIA score ≥ 11 , a segmental MaRIA score < 11 , or a decrease from baseline in segmental MaRIA score \geq MDD. For segments with baseline MaRIA score < 11 (but ≥ 7), a segmental MaRIA score < 7 or a decrease from baseline in segmental MaRIA score \geq MDD”.
- In the protocol, segment level disease stable is not defined.
In the SAP, the definition is “For segments with baseline MaRIA score ≥ 7 , absence of segment level MaRIA response and: if baseline MaRIA score ≥ 11 , no increase in segmental MaRIA score \geq MDD; if baseline MaRIA score < 11 , a segmental MaRIA score < 11 . For segments with baseline MaRIA score < 7 , no segment level disease worsening”.
- In the protocol, segment level disease worsening is not defined.
In the SAP, the definition is “An increase in segmental MaRIA \geq MDD with a segmental MaRIA score ≥ 7 at Week 24, or a segmental MaRIA score ≥ 11 at Week 24 while baseline MaRIA score < 11 ”.
- In the protocol, the definition of subject level small bowel MaRIA response states “All small bowel segments with baseline MaRIA score ≥ 7 achieve segment level MaRIA response, with no increase in MaRIA score \geq MDD in any other evaluable small bowel segment(s)”.
In the SAP, the definition is modified to “All small bowel segments with baseline MaRIA score ≥ 7 achieve segment level MaRIA response, with no segment level disease worsening in any other segment(s)”.
- In the protocol, the definition of subject with stable small bowel disease states “At least 1 small bowel segment doesn’t achieve segment level response, while no \geq MDD increase detected in any evaluable small bowel segment”.
In the SAP, the definition is modified to “At least 1 small bowel segment with baseline MaRIA score ≥ 7 doesn’t achieve segment level response, while no segment level disease worsening in any other evaluable small bowel segment(s)”.
- In the protocol, the definition of subject with small bowel disease progression states “At least 1 small bowel segment has MaRIA score > 11 , while \geq MDD increase in MaRIA score in at least 1 small bowel segment”.
In the SAP, the definition is modified to “At least 1 small bowel segment demonstrates segment level disease worsening”.

